- **MRI or CT** are the best currently available and reproducible methods to measure tumor lesions selected for response assessment. A **MRI or CT** scan should be performed with contiguous slice thickness of 5 mm or less. Subjects should be evaluated at screening for tolerance to **MRI/CT** IV contrast. Subjects intolerant of CT IV contrast (ie, allergy or renal insufficiency) should be imaged using non-contrast CT for the chest and MRI (with or without contrast) for the abdomen and pelvis to enable the best detection of disease throughout the study starting at baseline. If a subject develops a medical contradiction to the **MRI/CT** IV contrast while on study, preapproval of the sponsor is needed to switch from contrast enhanced **MRI** to non-contrast **MRI or to CT** (and vice versa).
- All baseline evaluations should be performed as closely as possible to the beginning of treatment and not more than 28 days before the beginning of the treatment (cycle 1 day 1).

Measurable disease: the presence of at least 1 measurable lesion. If the measurable disease is restricted to a solitary lesion, its neoplastic nature should be confirmed by cytology/histology.

- Measurable lesions:
 - Lesions with clear borders that can be measured accurately in two dimensions (longest perpendicular diameters $\geq 10 \times 10$ mm with **MRI/CT** scan slice thickness no greater than 5 mm).
 - Pathologic lymph nodes is measurable when the longest diameter perpendicular to the long axis (short axis) ≥ 15 mm.
- Non-measurable lesions:
 - All lesions not classified as measurable lesions. At baseline assessment, non-measurable lesions including small lesions that are smaller than 10×10 mm with **MRI/CT** slice thickness no greater than 5 mm)
 - Truly non-measurable lesions ie, bone lesions, pleural/pericardial effusions, leptomeningeal disease, ascites, inflammatory breast disease, lymphangitis cutis/pulmonis, cystic lesions, and abdominal masses that are not confirmed and followed by imaging techniques
 - Tumor lesions situated in a previously irradiated area
 - Pathologic lymph nodes with short axis ≥ 10 mm but < 15 mm
- Index lesions:

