 - All measurable lesions up to a maximum of 5 lesions per organ and 10 lesions in total, representative of all involved organs, are to be identified as Index lesions and recorded and measured. Index lesions are to be selected on the basis of their size and their suitability for accurate repeated measurements by imaging techniques, and most representative of the subject's tumor burden.
- Non-Index lesions:
 - Measurable lesions, other than index lesions, and all sites of non-measurable disease, will be identified as non-index lesions. Non-index lesions will be evaluated at the same assessment time points as the index lesions. In subsequent assessments, changes in non-index lesions will contribute only in the assessment of complete response.

- Pathologic lymph nodes with short axis ≥ 10 mm but < 15 mm should be considered as non-index lesions.
- Unable to evaluate (UE): Any lesion present at baseline which was not assessed or was unable to be evaluated leading to an inability to determine the status of that particular tumor for that time point.
- Not available (NA): Scan not available
- Not Done (ND): Radiographic image of clinical measurements were not performed at this time point to evaluate the index lesions.
- Index lesion response
 - Immune-related Complete Response (irCR) – complete disappearance of all index lesions in two consecutive observations at least 4 weeks apart
 - Pathologic lymph nodes must have reduction in short axis to ≤ 10 mm
 - Immune-related Partial Response (irPR) – decrease of 50% or greater in tumor burden compared with baseline in two consecutive observations at least 4 weeks apart
 - Immune-related Stable Disease (irSD) - not meeting the criteria for irCR or irPR, in the absence of immune-related progressive disease
 - Immune-related Progressive Disease (irPD) – at least a 25% increase in tumor burden compared with nadir (at any single time point) in two consecutive observations at least 4 weeks apart
 - When the size of the tumor lesion is considered 'too small to measure' (eg, less than 5×5 mm), a default value of 5×5 mm should be assigned for index lesions. If this is nadir, irPD will be judged from the tumor burden calculated using the default value.
- Non-Index Lesion Response
 - irCR – complete disappearance of all non-index lesions.
 - Pathologic lymph nodes must have reduction in short axis to < 10 mm
 - irPR – non-Index lesions are not considered in the definition of irPR

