 - irSD – non-Index lesions are not considered in the definition of irSD
 - irPD – increases in number or size of non-index lesion(s) does not constitute progressive disease. New lesions that are measurable ($\geq 5 \times 5$ mm, up to 5 new lesions per organ) are included in the calculation of tumor burden in response assessments.
- Overall response
 - irCR – complete disappearance of all lesions (whether measurable or not, and no new lesions).
 - Confirmation by a repeat, consecutive assessment no less than 4 weeks from the date of the first documented response
 - irPR – decrease in tumor burden $\geq 50\%$ relative to baseline.
 - Confirmation by a repeat, consecutive assessment at least 4 weeks after the first documentation

- irSD – not meeting criteria for irCR or irPR, in the absence of irPD
- irPD – increase in tumor burden $\geq 25\%$ relative to nadir (minimum recorded tumor burden).)
 - Confirmation by a repeat, consecutive assessment no less than 4 weeks from the date of the first documented assessment.
- Response confirmation:
 - irCR and irPR:
 - Must be confirmed by consecutive repeat assessments performed at least 4 weeks after the criteria for response are first met. The confirmation scan may also be performed at the next imaging assessment as defined by the schedule of assessment after the first observation.
 - irPD
 - Must be confirmed by consecutive repeat assessments performed at least 4 weeks apart in the absence of rapid clinical deterioration. The confirmation scan may also be performed at the next imaging assessment as defined by the schedule of assessment after the first observation if the subject has stable or improved clinical status. It is recommended that this be done at the discretion of the investigator because follow-up with observation alone may not be appropriate for subjects with a rapid decline in performance status.
 - Subjects with a global deterioration of health status requiring discontinuation of treatment without objective evidence of disease progression at the time should have the reason for treatment discontinuation classified as non-confirmed disease progression. In this case, irPD cannot be assigned at the time as the overall objective tumor response. Every effort should be made to document the objective progression even after discontinuation of treatment.

Measurement and Tumor Response Assessment Based on modified irRC	

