Measurable lesions	
 • $\geq 10 \times 10$ mm • Pathologic lymph nodes: short axis ≥ 15 mm
Measurement of each lesion	The product of the 2 longest perpendicular diameters (cm^2)
The sum of the measurements (SPD)	
 • The sum of the products of the 2 longest perpendicular diameters (SPD) of all index lesions and new measurable lesions if any • Up to 5 lesions per organ and up to 10 total index lesions
Response assessment	
 • irPD: $\geq 25\%$ increase from nadir (require confirmation) • irSD: $< 50\%$ decrease from baseline and $< 25\%$ increase from nadir • irPR: $\geq 50\%$ decrease from baseline (require confirmation) • irCR: Disappearance of all lesions (require confirmation)
New Lesions	
The presence of new lesion(s) does not define progression.
 
Measurable new lesions ($\geq 5 \times 5$ mm): The measurements of the new lesion(s) are included in the sum of the measurements.

Confirmation	Confirmation by 2 consecutive observations at least 4 weeks apart required for irCR, irPR, and irPD.

Modified irRC Overall Response Assessment			
Measurable Response	Non-measurable Response		Overall Response
Index and new, measurable lesions (tumor burden), ^a %	Non-Index lesions	New, non-measurable lesions	Using irRC
$\downarrow 100\%$	Absent	Absent	irCR ^b
$\downarrow 100\%$	Stable/NA	Any	irPR ^b
$\downarrow 100\%$	Unequivocal progression	Any	irPR ^b
$\downarrow \geq 50\%$	Absent/Stable/NA	Any	irPR ^b
$\downarrow \geq 50\%$	Unequivocal progression	Any	irPR ^b
$\downarrow < 50\%$ to $\uparrow < 25\%$	Absent/Stable/NA	Any	irSD
$\downarrow < 50\%$ to $\uparrow < 25\%$	Unequivocal progression	Any	irSD
$\uparrow \geq 25\%$	Any	Any	irPD ^b
UE	Any	Any	UE
ND	Any	Any	UE
NA	Any	Any	UE

NA = not available; ND = not done; UE = unable to evaluate

^a Decreased disease relative to baseline, including new measurable lesions ($\geq 5 \times 5$ mm)

^b Response (irCR, irPR) and progression (irPD) are confirmed by a second, consecutive assessment at least 4 weeks apart.

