Time to progression is calculated as the number of days from the first administration of AMG 211 to the first objective assessment of disease progression as per modified irRC or if applicable date of censoring (date of progressive disease or censoring – date of study day 1 +1). Time to progression will incorporate the independent radiologic review and/or the Investigator-reported assessment.

The following censoring strategies for missing assessment dates will be used for the time to progression analysis:

If a subject's disease has not progressed and the subject is alive, time to progression will be censored at the last date they are known to be progression-free (ie, the last evaluable radiological assessment date).

If a subject has died, time to progression will be censored at the date of death.

If a subject has no tumor evaluation in the study, progression-free survival time will be censored at the date of the first administration of AMG 211.

Subjects who withdraw consent to participate in the study prior to disease progression will be censored at their last evaluable radiological assessment date.

Time to Response

Time to response is calculated as the number of days from the first administration of AMG 211 to the first objective assessment of response as per modified irRC or if applicable date of censoring (date of first response or censoring – date of study day 1 +1).

The following censoring strategies for missing assessment dates will be used for the time to response analysis:

If a subject did not respond, time to response will be censored at the latest evaluable radiological assessment date.

If a subject has no tumor evaluation in the study, time of response will be censored at the date of the first administration of AMG 211.

Tumor Burden

Tumor burden is derived as the sum of the products of the 2 longest perpendicular diameters (SPD) of all index lesions (5 lesions per organ and up to 10 total lesions) and new measurable lesions ($\geq 5 \times 5$ mm; up to 5 new lesions per organ and 10 total lesions) if any, per irRC guidelines.

- Tumor burden = $SPD_{\text{index lesions}} + SPD_{\text{new, measurable lesions}}$

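### Appendix D's nodal rule for irCR cannot operate through its own overall-response table: a resolved but still visible index node is scored irPR, or in a narrow size range irSD

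*Protocol*

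**What the plan says.** All protocol references are to Appendix D.

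- **Entry.** "Pathologic lymph nodes is measurable when the longest diameter perpendicular to the long axis (short axis") is at least 15 mm, so nodes can be index lesions and can be a subject's only index disease. Nodes with a short axis of 10 mm to under 15 mm are still called pathologic, but are non-index.
- **Index lesion response.** irCR means that the index lesions are gone, with a sub-bullet for nodes: "Pathologic lymph nodes must have reduction in short axis to" ≤ 10 mm. The matching sub-bullet for non-index lesions says < 10 mm.
- **Overall response.** irCR is "complete disappearance of all lesions (whether measurable or not, and no new lesions"). The nodal sub-bullet is not repeated. The measurement table has "irCR: Disappearance of all lesions (require confirmation"), again without a nodal exception.
- **Overall-response table.** Under the column "Index and new, measurable lesions (tumor burden"), irCR appears only on the row with a 100% fall, non-index lesions absent and no new non-measurable lesions.
- **The sum.** It is "The sum of the products of the 2 longest perpendicular diameters (SPD) of all index lesions and new measurable lesions if any". SAP Section 6 agrees: "Tumor burden is derived as the sum of the products of the 2 longest perpendicular diameters (SPD) of all index lesions". Neither document gives a value of zero to a node that has returned to normal size.
- **irPR and irSD.** irPR is a "decrease of 50% or greater in tumor burden compared with baseline in two consecutive observations at least 4 weeks apart". irSD is a fall of under 50% with a rise of under 25%.

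SAP Section 6 defines complete response by reference to Appendix D. SAP Section 10.6.2 tabulates irCR, irPR, irSD and irPD separately and gives ORR with an exact 80% interval.

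**The concern.** A node that responds fully does not vanish; it returns to normal size and can still be measured. The nodal sub-bullet recognises this, but the overall definition and the table do not. Someone applying the sub-bullet would record irCR; someone applying the table would not. Both the sites and the imaging core laboratory assess response under these criteria (protocol Section 7.3.6), and the SAP takes best overall response from the investigator and/or the independent assessment, so the two sources can follow different parts of the same appendix.

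At stake are the irCR and irPR counts in the best-overall-response table and, in some cases, whether a subject counts in ORR at all. ORR is a secondary endpoint, but the trial's stated hypothesis is that objective responses will be seen.

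**Working it through.** **Inputs.** From Appendix D: smallest nodal index lesion, 15 mm short axis; nodal irCR threshold, ≤ 10 mm (index); table cut-offs of 100% (irCR) and 50% (irPR). From protocol Section 10.2: 39 subjects, ORR 20.5%, 80% CI 12.3% to 31.2%, half-width 9.5%. The change in long axis is not given, so it is an assumption here, shown over a range.

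**1. The plan's own figure.** 8/39 = 20.5%. The Clopper-Pearson 80% limits are the 10% quantile of Beta(8, 32) and the 90% quantile of Beta(9, 31): 12.3% and 31.2%. The half-width is 9.4% unrounded, or (31.2 − 12.3)/2 = 9.45% from the rounded limits. The stated interval is reproduced.

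**2. Can the table give irCR?** Let s0 and s1 be the baseline and follow-up short axes, and k the ratio of follow-up to baseline long axis. For a sole index node:

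fall in SPD = 1 − (s1 × k)/s0

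A visible node has s1 > 0 and k > 0, so the fall is below 100%. The irCR row cannot be reached.

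**3. Which row applies instead?** irPR needs k ≤ 0.5 × s0/s1. With the follow-up short axis at 10 mm:

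| Baseline short axis | k = 1.00 | k = 0.90 | k = 0.80 | k = 0.75 | Proportional (k = 10/s0) |
|---|---|---|---|---|---|
| 15 mm | 33.3% irSD | 40.0% irSD | 46.7% irSD | 50.0% irPR | 55.6% irPR |
| 16 mm | 37.5% irSD | 43.8% irSD | 50.0% irPR | 53.1% irPR | 60.9% irPR |
| 18 mm | 44.4% irSD | 50.0% irPR | 55.6% irPR | 58.3% irPR | 69.1% irPR |
| 20 mm | 50.0% irPR | 55.0% irPR | 60.0% irPR | 62.5% irPR | 75.0% irPR |

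Proportional shrinkage gives irPR even from the smallest eligible node (15 × 15 to 10 × 10 mm, 55.6%). From 20 mm upward, irPR is met with no long-axis change. Barring long-axis growth, irSD is confined to baselines of 15 to under 20 mm.

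A case resolved under both nodal cut-offs: 16 × 20 to 9 × 18 mm gives 1 − 162/320 = 49.4%, irSD. Here k = 0.90, and irPR needs k ≤ 0.5 × 16/9 = 0.889.

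**4. Mixed disease.** If non-nodal index lesions vanish as well, their SPD leaves the numerator but stays in the baseline, so the fall is larger. Adding a vanished 10 × 10 mm lesion to the last example gives 1 − 162/420 = 61.4%, irPR. irCR is still out of reach.

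**5. The cut-offs at exactly 10 mm.** An index node of 10 mm satisfies ≤ 10 mm, a non-index node of 10 mm fails < 10 mm, and a 10 mm node is pathologic under the ≥ 10 mm definition. The same index node is both resolved and pathologic.

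**6. Effect of one subject on ORR.** If one of 8 responders is scored irSD, ORR becomes 7/39 = 17.9%, 80% CI 10.3% to 28.3%. The shift is 1/39 = 2.6 percentage points.

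**The case against.** The strongest reply is that the nodal line sits as a sub-bullet under disappearance, for index and non-index lesions alike, and so defines what disappearance means for a node. The non-index entry of absent in the table must work that way, or the < 10 mm rule would have no use. Since irSD is what remains when irCR and irPR are not met, a node meeting the nodal rule would then not be irSD. This is probably what was intended. It does not repair the table, whose irCR row is set by a percentage fall in an SPD that still counts the node.

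Three further points have force. The irSD examples are near the boundary: 16 × 20 to 9 × 17 mm would be 1 − 153/320 = 52.2%, irPR. The core laboratory's Imaging Manual, which is not among the documents, may already settle nodal handling. And a shift of 2.6 points is well inside the planned 80% interval. These limit the size of the problem, but they leave the contradiction in Appendix D, to which the SAP defers.

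**Conclusion.** The point stands in a limited form. The nodal irCR rule and the overall definition and table contradict each other, and nothing in the two documents reconciles them. A subject with resolved but visible index nodes, and all other lesions gone, cannot be scored irCR by the table.

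A reader might infer that resolved node-only subjects are scored irSD and drop out of ORR. The documents do not support that as a general statement: because SPD multiplies two diameters, roughly proportional shrinkage clears 50% from any eligible starting size. The usual result is irCR recorded as irPR, which changes the best-overall-response table and leaves ORR alone. Calling this usual rests on the assumption that the long axis shrinks broadly in step with the short axis. Loss from ORR needs a baseline short axis of 15 to under 20 mm and limited long-axis shrinkage. Its frequency cannot be estimated, since the documents give neither the share of node-only subjects nor any long-axis data.

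A reader might also infer that small new nodes will push subjects to irPD under the 5 × 5 mm rule for new lesions. Appendix D does not say that a non-pathologic node is a lesion, and irPD needs confirmation, so that is not part of this point.

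**What to change.** In the overall irCR text and the table of Appendix D, state that index and non-index nodes meeting the nodal threshold count as disappeared or absent for irCR, whatever nodal SPD remains. Use one nodal cut-off for both kinds of node, consistent with Appendix D's own definition of a pathologic node; since that starts at 10 mm, the consistent choice is < 10 mm. The SAP inherits the change through its reference to Appendix D, and the Imaging Manual should be checked for agreement.

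One consequence should be accepted knowingly: an index node ending at exactly 10 mm would no longer count as resolved. For example, 15 × 20 to 10 × 16 mm (1 − 160/300 = 46.7%) would stay irSD.

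The cost is wording only. Both diameters are already recorded, so no new scans or measurements are needed.

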Appendix E. Toxicity Probability Interval (TPI) Bayesian Design

The dose-escalation cohorts will use a TPI Bayesian design to guide dose escalation. The MTD target TPI for DLT is (0.20, 0.35), and TPIs of (0.35, 0.60) and (0.60, 1.00) are defined as excessive and unacceptable, respectively. The design seeks to identify a dose most likely to have a DLT rate in the target TPI, but with overdose control that limits the possibility that the dose has an excessive or unacceptable DLT rate (Babb et al, 1998). The probability of a DLT at dose level d_i is assumed to follow a Bernoulli distribution with probability p_i where the logit of p_i increases linearly with the log of the standardized dose in the following 2-parameter logistic model:

$$\log [p_i / (1-p_i)] = \text{logit}(p_i) = \log[a] + \exp(\log[b]) \log (d_i / d_{\max})$$

where a and b are random variables and d_{\max} is the maximum planned dose.

A minimally informative prior distribution (Neuenschwander et al, 2008) was selected for $\theta = (\log a, \log b)$ where the probability that the true DLT rate is ≤ 0.60 at the lowest dose (200 $\mu\text{g}/\text{day}$ for 7 days) is 0.90 and the probability the true DLT rate is ≤ 0.20 at the maximum dose (6400 $\mu\text{g}/\text{day}$ for 14 days) is 0.21. Median values for p_i were interpolated per the logistic model. For each d_i , 2 quantiles for p_i were selected from a Beta distribution with the target median and a precision < 2 . This set of quantiles fully specified a target prior for θ . A bivariate normal distribution for θ was assumed where $(\log a)$ has a normal distribution with mean ma and standard deviation sa , and $(\log b)$ has a normal distribution with mean mb and standard deviation sb , and r is the correlation between $(\log a)$ and $(\log b)$. Numerical integration was used to calculate $\Pr[p_i \leq q(d_i)]$, where $q(d_i)$ is a quantile for dose d_i . An optimal bivariate normal distribution was estimated that achieved the minimum sum of squared difference between achieved and specified quantiles across all doses. The bivariate normal distribution prior solution has $ma = 0.0536$, $sa = 1.685$, $mb = -0.1469$, $sb = 1.001$, and $r = -0.216$.

The operating characteristics of the TPI Bayesian design were evaluated via simulation. The cohort size was fixed to be 3 subjects. All simulated studies started with an initial dose of 200 $\mu\text{g}/\text{day}$ for 7 days and subsequent doses were selected based on the rules specified in [Section 10.3.1](#).

The design was evaluated for two possible dose-response scenarios consistent with the design's model: "Low" and "High" MTDs. The target MTD of these 2 scenarios are set to be 1/3, and this target was set at a dose of 400 $\mu\text{g}/\text{day}$ for 14 days, and 3200 $\mu\text{g}/\text{day}$ for 14 days for the Low High scenarios, respectively. An "acceptable" final dose was

defined as one with the highest or second highest target TPI probability and a less than 0.25 excessive or unacceptable TPI probability. The acceptable doses by scenario were 200, 400 for Low and 1600, 3200 for High. The bivariate normal distribution for each scenario was estimated as per the prior. A Bernoulli probability for each subject in the simulations was selected from a random sample for the bivariate normal distribution for a given scenario, and a random DLT outcome for the subject was generated based on this DLT probability.

The simulation results are summarized in the table below. The average sample size increased from 15.7 to 20.8 in Low to High MTD scenarios. Early DLTs resulted in close to 5% chance of stopping with no dose selection in both cases due to the over-dose control criteria. The average Low and High final dose was about 360 and 1600 µg/d. The rate of acceptable dose selection is higher in Low scenario (83.1%), comparing with High scenario (51.4%). The average number of DLTs and DLT rate is higher in Low scenario than High scenario due to early occurrence of DLTs.

Simulation Results of TPI Model

	Low Acceptable Dose: 200, 400	High Acceptable Dose: 1600, 3200
Number of Subjects (IQR)	15.7 (15, 18)	20.8 (18, 24)
Acceptable Rate (95% CI)	83.1% (80.6%, 85.4%)	51.4% (48.3%, 54.5%)
No Dose Rate (95% CI)	4.5% (3.3%, 6.0%)	3.7% (2.6%, 5.1%)
Dose (IQR)	358.0 (200, 400)	1583.8 (800, 1600)
Number of DLTs (IQR)	3.8 (2, 4)	3.1 (2, 4)
DLT Rate	24.1%	15.0%

CI = confidence interval; DLT = dose-limiting toxicity; IQR = interquartile range

